6.4.2 Blood Sampling Time Points, Handling and Labelling of Blood Samples

Blood samples for PK evaluation will be collected by venepuncture (or by using an indwelling catheter). A blood volume of 5 mL will be drawn per timepoint.

Blood is drawn for PK analysis according to the schedule below, where timepoints are relative to IM injection of teverelix TFA at time zero, and the pre-dose PK sample is collected within 30 minutes prior to IM injection (Table 13).

Handling and labelling of blood samples for PK analysis will be performed according to the instructions provided by the central analytical laboratory. Special tubes, labels, packaging, and instructions for storage and shipment will also be provided by the analytical laboratory. Blood samples should be shipped for analysis on the day of collection.

Blood teverelix TFA concentrations will be determined from all collected samples using a validated sensitive analytical procedure (e.g. inductively coupled plasma mass spectrometry) at a specialised central analytical laboratory.

After completion of all analyses, any leftover blood or blood samples will be destroyed immediately after termination of the study.

Stability data supports the storage of teverelix PK samples:

- In a freezer set at nominally -20°C for up to 376 days
- In a freezer set at nominally -80°C for up to 60 days

Table 13: Pharmacokinetic Timepoints

Timepoi	Pre-	1	1.5	2	2.5	3	4	8	12	18	24	48	72
nt	dose	h	h	h	h	h	h	h	h	h	h ^a	h	h
Window	±0	±1	±1	±15	±15	±15	±15	±15	±15	±15	±15	±1	±1
	day	5	5	min	hou	hou							
		mi	mi									r	r
		n	n										
	•	•	•	•	•	•	•	•	•	•	•	•	•

Timepoin t	Da y 4 ^b	Da y 7 ^b	Da y 10 ^b	Da y 12 ^b	Da y 14 ^b	Da y 21 ^b	Day 28°	Day 35	Thereafter at each dosing visit and follow up visits ^d
Window	±0	±0	±1	±1	±1	±1	±3	±3	±3 days
	day	day	day	day	day	day	day	day	
							S	S	
	•	•	•	•	•	•	•	•	•

PK=pharmacokinetic

6.5 **Pharmacodynamics**

The following parameters will be investigated:

- T
- LH
- FSH
- PSA

^a Participants will remain in the clinic as in-participants until after the 24-hour PK blood sample has been drawn after which time they will be discharged.

^b From Day 4 onwards, when a PK sample is to be drawn on a non-dosing day, the PK sample should be drawn at the same time of day as the Day 0 pre-dose PK sample was drawn (+ 1 hour).

^c Before dosing (up to 30 minutes pre-dose). Dosing should be done at the same time of day throughout the study (or at least + 1 hour of this timepoint).

^dIncluding Day 203 to Final Assessment visits for Group 2 subjects

Table 14 presents the PD blood sampling schedule for the study.

Table 14: Pharmacodynamic Blood Sampling Schedule^a

	Day 0 (pre- dose)	24h	48h	72h	Day 4	Day 7	Day 10	Day 12	Day 14	Day 21 ^b	Day 28	Day 35°	Thereafter 7 days prior to each dosing visit	Thereafter at each dosing visit and follow up visits ^d
T (local)										•		•	•	•
T (central)	•	•	•	•	•	•	•	•	•	•	•	•		•
LH	•	•	•	•	•	•	•	•	•	•	•	•		•
FSH	•	•	•	•	•	•	•	•	•	•	•	•		•
PSA	•			·		•			•	•	•	•		•

FSH=follicle stimulating hormone; hs=high-sensitivity; LH=luteinising hormone; PD=pharmacodynamic; PK=pharmacokinetic; PSA=prostate-specific antigen; T=testosterone

^a PD blood draws should be done at the same time of day as PK blood draws (pre-dose on Day 0)

^b If PSA is <0.06 ng/mL hs PSA will be measured and reported. If PSA is ≥0.06 ng/mL then hs PSA will not be measured and reported.

^c Group 1 only

^dIncluding Day 203 to Final Assessment Visit for Group 2 subjects

7 Study Conduct

7.1 **Study Schedule**

Table 15 presents the study schedule for Groups 1 and 2.

Table 15: Schedule of Assessments for Groups 1 and 2

Visit/	Screeni							7	reatn	nent P	eriod (Group	s 1 &	2							Follo	Unsche
Procedure	ng					Sta	ge 1								\$	Stage 2	2				w-up	d. Visit
Days/		Da	Da	Da	Da	Da	Da	Da	Da	Da	Da	Da	Da	Da	Da	Da	Da	Da	Da	Da	28	
Weeks		y 0	y 1	y 2	y 3	y 4	y 7	y	y	y	y	y	y	y	y	y	y	y	y	y	days	
			,		·		,	10	12	14	21	28	35	42	77	84	11	12	16	16	after	
																	9	6	1	8	last	
																					dose	
Visit	V1	V2	V3	V4	V5	V6	V7	V8	V9	V1	V1	V1	V1	V1	V1	V1	V1	V1	V1	V2	V21	
Number										0	1	2	3	4	5	6	7	8	9	0		
Window	D-6 To -	±0	±0	±0	±0	±0	±0	±1	±1	±1	±1	±3	±3	±3	±3	±3	±3	±3	±3	±3	±3 D	
	1	D	D	D	D	D	D	D	D	D	D	D	D	D	D	D	D	D	D	D		
Informed																						
Consent																						
Inclusion																						
and	•																					
Exclusion																						
Criteria																						
Medical	•																					
History																						
Physical	•											•		•		•		•		•	•	
Exam.																						
12-Lead	•	•										•		•		•		•		•	•	•
ECG ¹																						
Holter																						
ECG		•	•																			
(Group 2																						
only)																						
Safety Labs ¹	•	•										•		•		•		•		•	•	
	•													•		•		•		•	•	
Vital Signs	•	-												•		•		•		-	•	•
Demograp hy ²	•	٠										•		•		•		•		•	•	•

¹ Safety laboratory tests are detailed in Section 6.3.5.

² Demographic details include height, weight, year of birth and age; During baseline and other visits including follow up (28 days after last dose) height, weight and BMI only will be measured.

Visit/	Screeni]	reatn	nent P	eriod (Group	s 1 &	2							Follo	Unsche
Procedure	ng					Sta	ge 1								,	Stage 2	2				w-up	d. Visit
Days/		Da	Da	Da	Da	Da	Da	Da	Da	Da	Da	Da	Da	Da	Da	Da	Da	Da	Da	Da	28	
Weeks		y 0	y 1	y 2	y 3	y 4	y 7	y	y	y	y	y	y	y	y	y	y	y	y	y	days	
								10	12	14	21	28	35	42	77	84	11	12	16	16	after	
																	9	6	1	8	last	
																					dose	
Visit	V1	V2	V3	V4	V5	V6	V7	V8	V9	V1	V1	V1	V1	V1	V1	V1	V1	V1	V1	V2	V21	
Number										0	1	2	3	4	5	6	7	8	9	0		
Window	D-6 To -	±0	±0	±0	±0	±0	±0	±1	±1	±1	±1	±3	±3	±3	±3	±3	±3	±3	±3	±3	±3 D	
	1	D	D	D	D	D	D	D	D	D	D	D	D	D	D	D	D	D	D	D		
Injection of																						
teverelix		•																				
TFA IM ³																						
Injection of																						
teverelix		•												•		•		•		•		
TFA SC																						
Blood draw																						
for pre-																						
dosing	•										•		•		•		•		•			
local lab T																					I I	
testing																						

³ IM injection and SC injection of teverelix TFA will be given immediately sequentially (within 10 minutes of each other); IM first; all PK time points detailed relative to the IM injection time. Participants to be monitored for hypersensitivity reaction for 30 minutes following SC injection.

Visit/	Screeni]	Freatn	nent P	eriod	Group	os 1 &	2							Follo	Unsche
Procedure	ng					Sta	ge 1									Stage 2	2				w-up	d. Visit
Days/		Da	Da	Da	Da	Da	Da	Da	Da	Da	Da	Da	Da	Da	Da	Da	Da	Da	Da	Da	28	
Weeks		y 0	y 1	y 2	y 3	y 4	y 7	y	y	y	y	у	y	y	y	y	y	y	y	y	days	
		Ů				,		10	12	14	21	28	35	42	77	84	11	12	16	16	after	
																	9	6	1	8	last	
																					dose	
Visit	V1	V2	V3	V4	V5	V6	V7	V8	V9	V1	V1	V1	V1	V1	V1	V1	V1	V1	V1	V2	V21	
Number										0	1	2	3	4	5	6	7	8	9	0		
Window	D-6 To -	±0	±0	±0	±0	±0	±0	±1	±1	±1	±1	±3	±3	±3	±3	±3	±3	±3	±3	±3	±3 D	
	1	D	D	D	D	D	D	D	D	D	D	D	D	D	D	D	D	D	D	D		
PK/PD							• 🖘	• 🖜	• 🖘	• 🖘	• 🖘	• 🖜	• ☜	• 🖜		• 🖜		•%		● 🟐		
Blood																						
Draw ⁴																						
												╚		╚				묘				
							≎	≎	≎	≎	≎	≎	≎	≎		₽		≎		≎		
							m,	M,	M,	m,	M,	M,	m,	m,		m,		m,		m,		
							×	×	×	×	×Λ	×̄	×Λ	×		×		×		×		
							m,	m,	M,	m,	m,	M,	m,	m,		m,		m,		m,		
							m,	M,	M,	m,	M,	M,	m,	m,		M,		m,		m,		
		● 5	•6	•7	•8	•9	mp	mp	mp	m	mp	щ	mp	m my		mp		m my		mp		
		ľ					M,	m,	m,	m,	m,	m,	m,	m,		m,		m,		m,		
							+□	•□	•□	•□	•□	•□	•□	•□		+ 🗖		•□		•□		
							•	•	•	•	•	♦	•	•		•		•		•		
							mp	m	m	m	m	m)	m	m		m		Щ		mp		
							m,	m,	m,	m,	m,	M,	m,	m,		m,		m,		m,		
												II										
																						l I
							♦	♦	•	→	♦	→	♦	•		♦		•		♦		
							Ϋ́	Ż	Ϋ́	Ŕ	Ϋ́	خر	اح	احر		اخر		بخر		, X		
							•	•	•	→	•	I →	•	→		•		•		•		
										ľ	Ě	lě		Ě				Ě				l I
							2	2	2	٦	2	ء ا	٦	٦		٦		٦		٦		

⁴ On Day of dosing visit, blood samples for PK/PD analysis will be collected before the administration of the Maintenance Dose.

Visit/	Screeni]	Γreatn	nent P	eriod (Group	s 1 &	2							Follo	Unsche
Procedure	ng					Sta	ge 1								\$	Stage 2	2				w-up	d. Visit
Days/		Da	Da	Da	Da	Da	Da	Da	Da	Da	Da	Da	Da	Da	Da	Da	Da	Da	Da	Da	28	
Weeks		y 0	y 1	y 2	y 3	y 4	y 7	y	y	y	y	y	y	y	y 77	y	y	y	y	y	days	
								10	12	14	21	28	35	42	77	84	11	12	16	16	after	
																	9	6	1	8	last	
																					dose	
Visit	V1	V2	V3	V4	V5	V6	V7	V8	V9	V1	V1	V1	V1	V1	V1	V1	V1	V1	V1	V2	V21	
Number										0	1	2	3	4	5	6	7	8	9	0		
Window	D-6 To -	±0	±0	±0	±0	±0	±0	±1	±1	±1	±1	±3	±3	±3	±3	±3	±3	±3	±3	±3	±3 D	
	1	D	D	D	D	D	D	D	D	D	D	D	D	D	D	D	D	D	D	D		
PSA/hs											•											
PSA^{10}		'					•			•	•	•	•	•		•		•		•		
Cardiac																						
biomarkers		'										•		•		•		•		•		
Injection																						
Site		•	•	•	•	•	•	•	•	•	•	•		•		•		•		•	•	
Inspection																						
Injection																						
Site																						
Photograph		•	•	•	•	•	•	•	•	•	•	•		•		•		•		•	•	
k																						
Prior and																						
current																						
Concomita	_		_	_	_		_	_	_	_						_		_		_		
nt	•	•	•	•	•	•	•	•	•	•	•	•		•		•		•		•	•	Ι.
Medication																						
S																						

⁵ Post-dose PK blood sampling on Day 0 is scheduled at the following time points: at 1, 1.5, 2, 2.5, 3, 4, 8, 12, 18 hours.

⁶ Post-dose PK blood sampling at 24 hours. At the time point of 24 hours post-dose sampling for PD analysis (T, LH, FSH) will be initiated.

⁷ Post-dose PK blood sampling at 48 hours.

 $^{^8}$ 72 hour PK profile: PD testing blood draw to be done at same time of day as the Day 0 pre-dose PK blood draw.

⁹ PK and PD testing blood draw to be done at same time of day as pre-dose PK blood draw.

¹⁰ If PSA is <0.06 ng/mL hs PSA will be measured and reported. If PSA is ≥0.06 ng/mL then hs PSA will not be measured and reported.

kIf a visible injection site reaction is present, two photographs should be taken and the better photograph uploaded to the eCRF

¹ECGs to be done in triplicate at each visit

Visit/	Screeni							7	reatn	nent P	eriod (Group	s 1 &	2							Follo	Unsche
Procedure	ng					Sta	ge 1								\$	Stage 2	2				w-up	d. Visit
Days/		Da	Da	Da	Da	Da	Da	Da	Da	Da	Da	Da	Da	Da	Da	Da	Da	Da	Da	Da	28	
Weeks		y 0	y 1	y 2	y 3	y 4	y 7	y	y	y	y	y	y	y	y	y	y	y	y	y	days	
								10	12	14	21	28	35	42	77	84	11	12	16	16	after	
																	9	6	1	8	last	
																					dose	
Visit	V1	V2	V3	V4	V5	V6	V7	V8	V9	V1	V1	V1	V1	V1	V1	V1	V1	V1	V1	V2	V21	
Number										0	1	2	3	4	5	6	7	8	9	0		
Window	D-6 To -	±0	±0	±0	±0	±0	±0	±1	±1	±1	±1	±3	±3	±3	±3	±3	±3	±3	±3	±3	±3 D	
	1	D	D	D	D	D	D	D	D	D	D	D	D	D	D	D	D	D	D	D		
Adverse	•																			•		
Events			-																			

BMI=body mass index; D=days; ECG=electrocardiogram; hs=high-sensitivity; IM=intramuscular; PD=pharmacodynamic; PK=pharmacokinetic; PSA=prostate-specific antigen; SC=subcutaneous; T=testosterone

Table 17: Schedule of Assessments for Group 2 (subjects with Stage 3 included)

Visit/	Screeni							T	`reatn	ent P	eriod	Grou	2 (w	ith Sta	age 3 (only)							Uns
Procedure	ng					Sta	ge 1								5	Stage 2	2				Sta	ige 3	ed
Days/ Weeks		Da y 0	Da y 1	Da y 2	Da y 3	Da y 4	Da y 7	Da y 10	Da y 12	Da y 14	Da y 21	Da y 28	Da y 35	Da y 42	Da y 77	Da y 84	Da y 11 9	Da y 12 6	Da y 16 1	Da y 16 8	Day 203	Follo w up Visit	Vis
Visit Number	V1	V2	V3	V4	V5	V6	V7	V8	V9	V1 0	V1 1	V1 2	V1 3	V1 4	V1 5	V1 6	V1 7	V1 8	V1 9	V2 0	V21	FA	
Window	D-6 To -1	±0 D	±0 D	±0 D	±0 D	±0 D	±0 D	±1 D	±1 D	±1 D	±1 D	±3 D	±3 D	±3 D	±3 D	±3 D	±3 D	±3 D	±3 D	±3 D	±3 D	±3 D	
Informed Consent	•																						
Inclusion and Exclusion Criteria	•	•																					
Medical History	•																						
Physical Exam.	•	•										•		•		•		•		•		•	
12-Lead ECG ¹	•	•										•		•		•		•		•		•	•
Holter ECG (Group 2 only)		•	•																				
Safety Labs ¹¹	•	•										•		•		•		•		•		•	•
Vital Signs	•	•										•		•		•		•		•		•	•

¹¹ Safety laboratory tests are detailed in Section 6.3.5.

[?] Demographic details include height, weight, year of birth and age; During baseline and other visits including follow up (28 days after last dose) height, weight and BMI only will be measured. *Subjects should attend on Day 203 and every 7 days until serum T levels are >1 ng/mL (local lab result). A final assessment visit should be conducted 7 days after serum T levels are >1 ng/mL (local lab result).

Visit/	Screeni							T	`reatn	nent P	eriod	Grou	2 (w	ith Sta	age 3 (only)						
Procedure	ng					Sta	ge 1									Stage 2	2				Sta	ige 3
Days/ Weeks		Da y 0	Da y 1	Da y 2	Da y 3	Da y 4	Da y 7	Da y 10	Da y 12	Da y 14	Da y 21	Da y 28	Da y 35	Da y 42	Da y 77	Da y 84	Da y 11 9	Da y 12 6	Da y 16 1	Da y 16 8	Day 203	Follo w up Visit
Visit Number	V1	V2	V3	V4	V5	V6	V7	V8	V9	V1 0	V1 1	V1 2	V1 3	V1 4	V1 5	V1 6	V1 7	V1 8	V1 9	V2 0	V21 *	FA
Window	D-6 To -1	±0 D	±0 D	±0 D	±0 D	±0 D	±0 D	±1 D	±1 D	±1 D	±1 D	±3 D	±3 D	±3 D	±3 D	±3 D	±3 D	±3 D	±3 D	±3 D	±3 D	±3 D
Demograp hy ¹²	•	•										•		•		•		•		•		•
Injection of teverelix TFA IM ¹³		•																				
Injection of teverelix TFA SC		•												•		•		•		•		
Blood draw for pre-dosing local lab T testing	•										•		•		•		•		•		•	

¹² Demographic details include height, weight, year of birth and age; During baseline and other visits including follow up (28 days after last dose) height, weight and BMI only will be measured.

*Subjects should attend on Day 203 and every 7 days until Day 252 or until serum T levels are >1 ng/mL (local lab result). A final assessment visit should be conducted on Day 259 or 7 days after serum T levels are >1 ng/mL (local lab result), Whichever occurs first.

¹³ IM injection and SC injection of teverelix TFA will be given immediately sequentially (within 10 minutes of each other); IM first; all PK time points detailed relative to the IM injection time. Participants to be monitored for hypersensitivity reaction for 30 minutes following SC injection.

Visit/	Screeni							T	reatn	nent P	eriod	Grou	p 2 (w	ith St									Unse
Procedure	ng						ge 1									Stage					Sta	ige 3	ed.
Days/ Weeks		Da y 0	Da y 1	Da y 2	Da y 3	Da y 4	Da y 7	Da y 10	Da y 12	Da y 14	Da y 21	Da y 28	Da y 35	Da y 42	Da y 77	Da y 84	Da y 11 9	Da y 12 6	Da y 16 1	Da y 16 8	Day 203	Follo w up Visit	Vis
Visit Number	V1	V2	V3	V4	V5	V6	V7	V8	V9	V1 0	V1 1	V1 2	V1 3	V1 4	V1 5	V1 6	V1 7	V1 8	V1 9	V2 0	V21 *	FA	
Window	D-6 To -1	±0 D	±0 D	±0 D	±0 D	±0 D	±0 D	±1 D	±1 D	±1 D	±1 D	±3 D	±3 D	±3 D	±3 D	±3 D	±3 D	±3 D	±3 D	±3 D	±3 D	±3 D	
PK/PD Blood Draw ¹⁴		•15	•16	•17	•18	•19						• № □□□□□□□□□□□▼▼□□□□□□□□□□□□□□□□□□□□□□□		·፼□□□□□□□□□□□□♥♥□♥♥□□□□□□♥♥□□□□□□□□□□□□							•	•	

¹⁴ On Day of dosing visit, blood samples for PK/PD analysis will be collected before the administration of the Maintenance Dose.

¹⁵ Post-dose PK blood sampling on Day 0 is scheduled at the following time points: at 1, 1.5, 2, 2.5, 3, 4, 8, 12, 18 hours.

¹⁶ Post-dose PK blood sampling at 24 hours. At the time point of 24 hours post-dose sampling for PD analysis (T, LH, FSH) will be initiated.

Visit/	Screeni							T	`reatn	nent P	eriod	Grou	2 (w	ith St	age 3 (
Procedure	ng					Sta	ge 1									Stage	2				Sta	ge 3
Days/ Weeks		Da y 0	Da y 1	Da y 2	Da y 3	Da y 4	Da y 7	Da y 10	Da y 12	Da y 14	Da y 21	Da y 28	Da y 35	Da y 42	Da y 77	Da y 84	Da y 11 9	Da y 12 6	Da y 16 1	Da y 16 8	Day 203	Follo w up Visit
Visit Number	V1	V2	V3	V4	V5	V6	V7	V8	V9	V1 0	V1 1	V1 2	V1 3	V1 4	V1 5	V1 6	V1 7	V1 8	V1 9	V2 0	V21	FA
Window	D-6 To -1	±0 D	±0 D	±0 D	±0 D	±0 D	±0 D	±1 D	±1 D	±1 D	±1 D	±3 D	±3 D	±3 D	±3 D	±3 D	±3 D	±3 D	±3 D	±3 D	±3 D	±3 D
PSA/hs PSA ²⁰		•					•			•	•	•	•	•		•		•		•	•	•
Cardiac biomarkers		•										•		•		•		•		•		•
Injection Site Inspection			•	•	•	•	•	•	•	•	•			•		•		•		•		•
Injection Site Photograph		•	•	•	•	•	•	•	•	•	•	•		•		•		•		•		•
Prior and current Concomita nt Medication s	•	•	•	•	•	•	•	•	•	•	•			•		•		•		•	•	•
Adverse Events	•	•	•	•	•	•	•	•	•	•	•	•		•		•		•		•	•	•

¹⁷ Post-dose PK blood sampling at 48 hours.

¹⁸ 72 hour PK profile: PD testing blood draw to be done at same time of day as the Day 0 pre-dose PK blood draw.

¹⁹ PK and PD testing blood draw to be done at same time of day as pre-dose PK blood draw.

²⁰ If PSA is <0.06 ng/mL hs PSA will be measured and reported. If PSA is ≥0.06 ng/mL then hs PSA will not be measured and reported.

11 If a visible injection site reaction is present, two photographs should be taken and the better photograph uploaded to the eCRF

12 ECGs to be done in triplicate at each visit

7.2 **Observations by Visit**

7.2.1 Screening Examination (Day -6 to Day -1)

At the screening examination the following will be carried out and/or documented:

- Participant signs ICF as a part of the written participant information including the agreement concerning protection of personal data and direct access to source documents
- Date of visit
- Demographic data (height, weight, year of birth, age)
- Diagnosis of study indication (specify duration, severity as requested)
- Relevant medical history for the past 5 years
- Pre-treatment during the past 6 months
- Concomitant disease(s) (including date of diagnoses), concomitant therapy(ies)
- Physical examination (see Section 6.3.2)
- 12-Lead ECG (see Section 6.3.3)
- Safety laboratory tests (fasted \geq 8 hours)
- Total T (local laboratory)
- HbA1c
- Vital signs
- Check of inclusion and exclusion criteria

Concomitant diseases are to be documented, taking into consideration the medical history of the participant for the past 5 years. Findings that are not medically relevant for the study are: operation scars, accident scars, and bad sight etc.

7.2.2 Baseline Examination (Day 0), Stage 1

At baseline examination the following will be carried out and/or documented:

- Date of visit
- Weight, and BMI
- Documentation of changes in concomitant diseases and/or concomitant therapies (also medication taken only once and any non-prescription medicine)
- AEs (for definition see Section 6.2.4)
- Check of inclusion and exclusion criteria
- Physical examination
- 12-Lead ECG
- Continuous 24 h, 12-lead Holter ECG (Subset of 30 Group 2 subjects only)
- Safety laboratory tests (fasted (≥8 hours))
- Vital signs
- Pre-dose blood sampling for PK, PSA and PD analysis
- Pre-dose blood sampling for cardiac biomarkers (Group 2 only)
- Administration of the loading dose of teverelix TFA, which consists of IM followed by SC injection
- ISI
- Post-dose PK blood sampling

Additional Visits for Pharmacokinetic and Pharmacodynamic Samplings during Stage 1:

- During Stage 1, the participant will return to the study site for additional PK and PD blood sampling at 24, 48 and 72 hours post-dose, and on Days 4, 7, 10, 12, 14, and 21
- On Day 21 local testing of T levels will be performed
- On Days, 7, 14, and 21, blood sampling for PSA will be performed

7.2.3 Treatment (Maintenance Dose) Period Visits (Day 28 to Day 168), Stage 2

At the treatment period visits, the following examinations will be carried out and/or documented:

- Date of visit
- Date and time of day when the medication was administered
- Documentation of changes in concomitant diseases and/or concomitant therapies (also medication taken only once and any non-prescription medicine)
- AEs (for definition see Section 6.3.7)
- Physical examination
- 12-Lead ECG
- Safety laboratory tests (fasted (≥8 hours))
- Vital signs
- Blood sampling for PK, PSA, and PD analysis (before administration of teverelix TFA) (see Table 15 and Error: Reference source not found)
- Pre-dose blood sampling for cardiac biomarkers (Group 2 only)
- ISI
- Administration of the maintenance dose of teverelix TFA, which consists of an SC injection

7.2.4 Follow-up Visit (28 Days after Last Dose)(Group 1 and Group 2 subjects without Stage 3)

At the final visit, the following examinations will be carried out and/or documented:

- Date of visit
- Documentation of changes in concomitant diseases and/or concomitant therapies (also medication taken only once and any medicine taken without a prescription)
- AEs
- Physical examination
- 12-Lead ECG
- Safety laboratory tests (fasted (≥8 hours))
- Blood sampling for PK, PSA, and PD
- Blood sampling for cardiac biomarkers (Group 2 only)
- ISI
- Vital signs
- Demography (only weight)
- Final assessment by investigator and participant

7.2.5 Follow-up Visits (starting 35 days after Last Dose)(Group 2 with Stage 3 subjects only)

Five weeks after the Day 168 maintenance dose injections (Day 203), subjects will attend the clinic and the following procedures will be done:

- Date of visit
- Documentation of changes in concomitant diseases and/or concomitant therapies (also medication taken only once and any medicine taken without a prescription)
- AEs
- Blood sampling for PK, PSA, and PD (local AND central lab serum T levels)

Subjects will continue to attend the clinic every 7 days where the above procedures will be done. Weekly visits will continue until Day 252 or until serum T levels (local lab result) are ≥ 1 ng/mL (local lab result) when the subject will attend the clinic 7 days later and the following procedures will be done:

- Date of visit
- Documentation of changes in concomitant diseases and/or concomitant therapies (also medication taken only once and any medicine taken without a prescription)
- AEs
- Physical examination
- 12-Lead ECG
- Safety laboratory tests (fasted (≥8 hours))
- Blood sampling for PK, PSA, and PD
- Blood sampling for cardiac biomarkers (Group 2 only)
- ISI
- Vital signs
- Demography (only weight)
- Final assessment by investigator and participant

7.3 **Duration of the Study**

The study will be terminated when all participants have completed the planned investigation period.

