SC=subcutaneous; T=testosterone; TFA=Trifluoroacetate For participants in Group 2, the following actions will be taken at the Day 28 visit based on the results of the locally analysed T level determined from the Day 21 visit:

[T] (ng/mL)	Action Taken	Dose Administered
≤2	Continue with Stage 2 of Group 2	No dose on Day 28. Maintenance dose of 180 mg SC teverelix TFA every 42 days
>2	Withdraw from study; safety follow-up visit on Day 28	None

SC=subcutaneous; T=testosterone; TFA=Trifluoroacetate

Day 35 Visit

On Day 35, local testing of T levels will be performed to guide decision making at the Day 42 visit. PK, total T, LH, FSH and PSA (total and high-sensitivity [hs]) samples will also be collected for central laboratory analysis.

Stage 2 Visits in Groups 1 and 2

Day 28 Visit

Stage 2 will start at the Day 28 visit. However, participants will receive their first maintenance dose at the Day 42 visit and participants will visit the clinic at Day 35 to provide a blood sample for local laboratory testing of T levels.

Blood samples for PK and PD analyses (T, LH, FSH, PSA), and fasted (≥8 hours) safety laboratory testing will be collected. Samples will also be collected for urine analysis. AE assessment, physical examination, triplicate 12-lead ECG and assessment of vital signs (including sitting blood pressure and heart rate) will be performed.

If, in the opinion of the investigator, no safety concerns exist, participants will be discharged from the centre.

Visits at Day 42, Day 84, Day 126, and Day 168

On Day 42 the first maintenance dose will be administered.

Before administration of the maintenance dose, blood samples for PK and PD analyses as well as fasted (≥8 hours) safety laboratory testing will be collected. Samples will also be collected for urine analysis. Pre-dose AE assessment (including ISR), physical examination, triplicate 12-lead ECG and assessment of vital signs (including sitting blood pressure and heart rate) will be performed.

Participants will attend the clinic 1 week before each maintenance dose is given (i.e. at Days 35, 77, 119 and 161) to provide a blood sample for local laboratory assessment of T levels. At the Day 35 visit (only) PK, total T, LH, FSH and PSA (total and hs) samples will also be collected for central laboratory analysis. Based on the results of the local analysis of T level from 7 days prior to the scheduled visit, participants will receive:

[T] (ng/mL)	Action Taken	Dose Administered

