1.2 Background Information on Investigational Medicinal Product

The investigational medicinal product (IMP) to be tested in this study is teverelix trifluoroacetate (TFA), a depot formulation of a GnRH antagonist used for the treatment of advanced prostate cancer. Treatment with the IMP will start with a loading dose administered

Page 28 of 84

through 2 injections, one of which will be given IM and the other of which will be given SC, followed by a maintenance SC injection every 4 or 6 weeks. Two treatment regimens will be tested in this study: 120 mg of teverelix TFA administered, after the loading dose, every 42 days and 180 mg of teverelix TFA administered, after the loading dose, every 42 days.

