DAY 21 [T]	DAY 28: No teverelix TFA dose
DAY 35 [T]	DAY 42: Maintenance dose 120 or 180 mg SC
DAY 77 [T]	DAY 84: Maintenance dose 120 or 180 mg SC
DAY 119 [T]	DAY 126: Maintenance dose 120 or 180 mg SC
DAY 161 [T]	DAY 168: Maintenance dose 120 or 180 mg SC
*DAY 203 [T]	No dose
*DAY 210 [T]	No dose
*DAY 217 [T]	No dose
*DAY 224 [T]	No dose
*DAY 231 [T]	No dose
*DAY 238 [T]	No dose
*DAY 245 [T]	No dose
*DAY 252 [T]	No dose

SC=subcutaneous; T=testosterone

^{*}Group 2 subjects with Stage 3 only

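### Protocol 7.2.3 and the PK sampling footnote treat Day 28 as a dosing visit, while the dosing tables in both documents show no dose that day; the texts must be reconciled

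*Protocol*

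**What the plan says.** **Text that treats Day 28 as a dosing visit**

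- Protocol 7.2.3 is headed "7.2.3 Treatment (Maintenance Dose) Period Visits (Day 28 to Day 168), Stage 2". Its procedure list includes "Administration of the maintenance dose of teverelix TFA, which consists of an SC injection". Other items in the list also presuppose an injection: recording when the medication was given, drawing PK and PD blood ahead of teverelix, and pre-dose biomarker sampling. Day 28 is not excepted.
- Protocol 6.4.2, Table 13, attaches footnote c to Day 28: "Before dosing (up to 30 minutes pre-dose". SAP Table 17 carries the same footnote on the same day.
- Protocol 1.2, in the background section, describes the loading dose as "followed by a maintenance SC injection every 4 or 6 weeks".

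**Text that shows no dose on Day 28**

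- The synopsis, under the Stage 2 Day 28 visit, says that "participants will receive their first maintenance dose at the Day 42 visit". The Day 28 action tables for Group 1 and Group 2 both state that nothing is given that day.
- Protocol Table 4 (section 5.5) and SAP Table 2 have the row "DAY 28: No teverelix TFA dose".
- Protocol Table 1 and SAP Table 1 give a 6-weekly interval.
- The subcutaneous-injection rows of the protocol's assessment schedules mark Days 0, 42, 84, 126 and 168.
- Protocol 6.3.1 names Days 42, 84, 126 and 168 as the maintenance-dose days, and 6.3.5 lists Day 28 separately from the Stage 2 dosing visits.

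**The concern.** Section 7.2 is the visit-by-visit part of the protocol, the text site staff would naturally open to run a visit. If it assigns an injection to Day 28 and the dosing tables do not, the protocol gives two answers to whether drug is administered at that visit.

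The statistical stake is the meaning of the Day 42 endpoints (secondary endpoints 2 and 3: testosterone below 0.5 and below 0.2 ng/mL). Under the dosing tables, the Day 42 pre-dose sample shows suppression at the end of the 42 days that follow the loading dose. After a Day 28 injection it would show something else. Day 35 and Day 42 values also enter the supplementary Kaplan-Meier analysis in SAP 6.8.3.

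**Working it through.** The plan states no figure on this point, so the check is a comparison of texts plus calendar arithmetic.

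**1. Does the 7.2.3 list fit Day 28?** In protocol Table 15, physical examination, ECG, safety laboratory tests, vital signs and cardiac biomarkers are marked within Stage 2 at Days 28, 42, 84, 126 and 168. None is marked at Days 35, 77, 119 or 161. Of the blood draws in the list, only PK/PD and PSA are also marked at Day 35. The local testosterone draw, which is the purpose of Days 77, 119 and 161, is not in the list. So the list describes Day 28 together with the four dosing visits, and it gives Day 28 the injection as well.

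**2. What does the footnote do?** In Table 13, footnote b covers samples on non-dosing days and is attached to Days 4 to 21. Day 28 carries footnote c, the pre-dose window, instead. The column for later dosing visits carries only footnote d, which concerns the Stage 3 visits. The 30-minute window therefore sits on a visit where Table 4 shows no dose and is absent from the visits where it shows one. Footnote 4 of Table 15 does require sampling before the maintenance dose, but it gives no window.

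**3. Calendar**

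| Reading | Maintenance days | Number |
|---|---|---|
| 42-day interval from Day 0 | 42, 84, 126, 168 | 4 (matches Table 4) |
| Same, plus Day 28 from 7.2.3 | 28, 42, 84, 126, 168 | 5 |
| 28-day interval | 28, 56, 84, 112, 140, 168 | 6 |

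No schedule has a visit on Day 56, 112 or 140, so the third row has no support in the visit plan.

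**4. Consequence for one participant, if a Day 28 dose were given**

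- Maintenance injections: 5 against 4, that is 5/4 − 1 = +25%.
- Time from that injection to the Day 42 sample: 42 − 28 = 14 days.
- Total dose, Group 1: 2×120 + 4×120 = 720 mg, against 2×120 + 5×120 = 840 mg.
- Total dose, Group 2: 2×180 + 4×180 = 1080 mg, against 2×180 + 5×180 = 1260 mg.
- Subcutaneous compliance under SAP 6.7: planned 1 + 4 = 5, given 6, so 6/5 = 120%.

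**5. Primary endpoint.** Section 7.2.3 and footnote c both place the Day 28 blood sample before any injection, so Day 28 testosterone is the same under either text.

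**The case against.** The strongest defence is that Day 28 dosing is settled expressly and repeatedly. At that visit the site must apply an action table that says no dose is given. Table 4 and the injection row of Table 15, to which 7.2.3 itself refers, say the same. A site would have to override all of these. This stands, and it is why the consequence can only be stated conditionally.

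A second argument is that 7.2.3 pools procedures for all Stage 2 visits and is no dosing calendar, since a literal reading would also put injections on Days 35, 77, 119 and 161. This is weaker. Step 1 of the working shows that the list matches Day 28 and the dosing visits, not the local-testosterone visits.

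A third is that footnote c times a sample and does not order a dose. That is correct, but it still classes Day 28 as a dosing day.

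Three stronger inferences are tempting and are not supported:

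- **That section 1.2 permits 4-weekly maintenance.** It is background text, and its next sentence gives 42 days for both regimens, for example "180 mg of teverelix TFA administered, after the loading dose, every 42 days".
- **That sites will give an extra dose and the Day 42 results will be lost.** Nothing in the documents shows that any participant would be affected.
- **That such a participant would leave the per-protocol set.** SAP 4.3.3 does not name an extra dose among its exclusion reasons, and SAP 3.7 leaves the major/minor criteria to be set before database lock. If he were excluded, his Day 42 value would not enter the per-protocol result, only the ITT repeat.

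**Conclusion.** The inconsistency is established: one visit instruction and one sampling footnote, the latter in both documents, conflict with a consistent set of dosing tables. Section 1.2 adds a minor leftover that contradicts itself within two sentences. Protocol Table 3 is not part of the conflict, because it names neither a day nor an interval.

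The size is conditional and per participant: one additional maintenance injection (five rather than four) and a Day 42 measurement taken 14 days after it. This assumes that a site follows 7.2.3 literally at Day 28 and then keeps to the rest of the Table 4 calendar. The number of participants affected cannot be estimated from the documents and may be zero. The primary endpoint is not at risk from this point.

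It is a defect of wording, worth correcting because it concerns when drug is injected. No view is taken on which dosing rule is clinically right.

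**What to change.** Settle the dosing visits and the interval once, and make protocol 7.2.3, footnote c of protocol Table 13 and SAP Table 17, and protocol 1.2 agree with the dosing tables on them. In 7.2.3, list by day the visits at which a dose is given, and separate the procedures that apply only there. Attach the pre-dose sampling window to the reconciled dosing visits, and give Day 28 whichever footnote matches its agreed status.

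If the dosing tables stand as written, this is wording in four places with no change to the data collected. Protocol 10.2 requires a formal amendment for any protocol change, so the edit is best combined with another amendment or, until then, covered by a written clarification to sites.
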